## **Study Protocol with Statistical Analysis Plan:**

### Study Design

A randomized crossover trial. Using a website (<http://www.randomization.com>), an independent researcher randomly allocated the subjects in three groups with a ratio of 1:1:1 and block sizes of 18. Then, concealed allocation results in sequentially numbered, opaque, sealed envelopes, and placed it in an agreed location. Another researcher opened the envelopes only before the first intervention, in the presence of the subject. Each group differs regarding arrangement application order, as follows: group A) coplanar, contraplanar and longitudinal; group B) contraplanar, coplanar and longitudinal; group C) longitudinal, coplanar and contraplanar.

The same researcher that captured the thermographic images color-coded the results, which were given to a blinded researcher for data analyses, who returned it afterwards for decoding. The researchers were kept blinded to the process in which they did not participate, and the subjects to the intensity indicator monitor.

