### Interventions

Each subject attended to three sessions with a washout period of at least 24 hours. In order to stabilize body temperature, subjects laid in a relaxed prone position on a wooden stretcher, under instruction to refrain from touching the left thigh over the 20 minutes of acclimatization. Then, the previous determined capacitive technic arrangement of SWD was applied for 20 minutes.

The SWD device we used was Diatermede II (Carci® 4022, São Paulo, SP, Brazil), on continuous mode, with a frequency of 27.12 MHz. Which was delivered by means of two pad electrodes (17x12 cm) surrounded by felt and positioned over 1 cm^6 of toweling. On coplanar arrangement, the electrodes were as far apart as the cross-sectional diameter of the pad electrode (Figure 1). We controlled the intensity based on a referred warm heat perception by the subject. The device was calibrated prior to data acquisition.

We measured the temperature in three time points, first: before the application (baseline), after acclimatization period, second: immediately after each application, and third: each minute over 25 minutes after electrodes removal. We maintained room temperature between 23 °C and 25 °C, with a mean humidity of 64% throughout the study. The room had no source of infrared radiation or airflow.

Previously to acclimatization period we had marked each 6 cm over 36 cm from the base of the patella towards the anterior superior iliac spine. We collected skin temperature under the electrode (at the centre of the proximal electrode), and at the thigh centre (6 cm from the proximal electrode's edge). Thus, on coplanar and longitudinal arrangement at 18 cm and 30 cm marks, and on contraplanar arrangement at 12 cm and 24 cm marks (Figure 2).

Outcomes Measures

The primary endpoint was to determine the most efficient arrangement of capacitive technic with respect to temperature change over the 25 minutes after application, which was measured in Celsius (°C) on the anterior aspect of the left thigh.

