#### Statistical Analysis

We used descriptive statistics to summarize data, computing means and standard deviations (SDs) for the primary endpoint, and the Shapiro-Wilk test for checking data normality. To compare the arrangements we conducted a repeated measures analysis of variance (ANOVA) and Bonferroni post-hoc tests. The  $\alpha$  level was set at  $<.05$ . Effect size was calculated through partial eta squared and correlated using Cohen index (.1 to .3 as small, .3 to .5 as medium, and over .5 as large). In order to summarize the data we conducted 5-minute interval analysis. SPSS software (version 20; IBM Corp, Armonk, NY) was used for analyzes.

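### The three treatment orders are not balanced over sessions and no session term is named, so arrangement is partly confounded with session

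*Combined protocol and SAP*

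**What the plan says.** The trial is a three-session crossover. The Study Design section states that an independent researcher "randomly allocated the subjects in three groups with a ratio of 1:1:1 and block sizes of 18", and the groups differ only in the order of application: "group A) coplanar, contraplanar and longitudinal; group B) contraplanar, coplanar and longitudinal; group C) longitudinal, coplanar and contraplanar".

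The Interventions section adds: "Each subject attended to three sessions with a washout period of at least 24 hours". It also describes how output was set on each occasion: "We controlled the intensity based on a referred warm heat perception by the subject". The Outcomes Measures paragraph in the same section gives the primary aim as finding "the most efficient arrangement of capacitive technic with respect to temperature change over the 25 minutes after application".

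The Statistical Analysis section reads: "To compare the arrangements we conducted a repeated measures analysis of variance (ANOVA) and Bonferroni post-hoc tests". Neither document section names a session, sequence or carry-over term, and no sample size or SD is given.

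**The concern.** In a crossover, the order scheme is meant to spread each treatment evenly over the sessions, so that anything changing from one session to the next falls equally on all treatments. The three listed orders do not do this. Longitudinal is given last in two of the three groups, and coplanar is given second in two of the three.

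An ANOVA with arrangement as its only named treatment-related factor would then read a difference between sessions 2 and 3 as a difference between arrangements. The primary question is a ranking of the arrangements, so the bias falls directly on the main conclusion. More subjects would not shrink it; they would make a false difference more likely to reach significance.

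**Working it through.** The plan gives no sample size, power or SD, so there is no figure of its own to reproduce. The counts, bias and relative precision below follow from the stated orders with equal groups. The false-positive rates need assumptions, which are marked.

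**1. Arrangement by session.** Counting over groups A, B and C (Study Design):

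| | Session 1 | Session 2 | Session 3 |
|---|---|---|---|
| Coplanar | 1 | 2 | 0 |
| Contraplanar | 1 | 1 | 1 |
| Longitudinal | 1 | 0 | 2 |

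**2. Bias without a session term.** Let p1, p2 and p3 be additive session effects. The contribution of session to each arrangement mean is:

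- coplanar: (p1 + 2·p2)/3
- contraplanar: (p1 + p2 + p3)/3
- longitudinal: (p1 + 2·p3)/3

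With d = p3 − p2, subtraction gives:

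- longitudinal − coplanar: (2/3)d
- contraplanar − coplanar: (1/3)d
- longitudinal − contraplanar: (1/3)d

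The p1 terms cancel, so only a difference between sessions 2 and 3 matters.

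**3. Precision once session is fitted.** Least squares with subject, arrangement and session, for 18 subjects (one complete block, 6 per order). Variances are in units of the within-subject variance σ²:

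| Contrast | Stated orders | Session-balanced orders | Variance ratio | SE ratio |
|---|---|---|---|---|
| Longitudinal − coplanar | 0.200 | 0.111 | 1.8 | √1.8 = 1.34 |
| Contraplanar − coplanar | 0.133 | 0.111 | 1.2 | √1.2 = 1.10 |
| Longitudinal − contraplanar | 0.133 | 0.111 | 1.2 | √1.2 = 1.10 |

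All contrasts remain estimable. Residual degrees of freedom go from 34 (54 observations − 20 parameters) to 32 (54 − 22). The ratios do not depend on the number of subjects.

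**4. False-positive rate of the unadjusted ANOVA (illustration).** Assumed: no true arrangement effect, one value per subject and session, 18 or 36 subjects (one or two blocks), and d in units of the within-subject SD. Simulated with 40,000 runs at nominal 5%:

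| Pattern | d = 0.25 | 0.5 | 0.75 | 1.0 |
|---|---|---|---|---|
| n = 18, only session 3 differs | 6.4% | 11.2% | 18.6% | 28.5% |
| n = 18, only session 2 differs | 6.5% | 11.2% | 18.5% | 28.4% |
| n = 18, linear drift of d per session | 5.8% | 7.6% | 9.4% | 10.4% |
| n = 36, only session 3 differs | 8.6% | 19.5% | 38.6% | 59.4% |
| n = 36, linear drift of d per session | 7.9% | 14.3% | 23.0% | 32.5% |

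If only session 1 differs, by the same shift sizes (so d = 0), the rate at n = 18 is 4.9%, 4.0%, 3.1% and 2.1%. With a session term fitted, it stayed between 4.6% and 5.7% in every pattern and at both sample sizes (10,000 runs).

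**5. Order group alone does not repair it.** If order group is added only as a between-subject factor, the arrangement means are still averaged equally over the three groups, so the bias in step 2 is unchanged. At n = 18 (2 and 30 df) the rates are 6.7%, 12.4%, 22.9% and 38.0% for the same four values of d, whatever session 1 does.

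**The case against.** The strongest reply is that the harm depends on one quantity the documents do not report. Bias arises only if the response differs between sessions 2 and 3; first-visit unfamiliarity cancels. The conditions are also well standardised: exercise, food and caffeine restrictions, 20 minutes of acclimatisation, a baseline at every session, a room at 23–25 °C without airflow, and at least 24 hours between sessions. This stands in part. Analysing change from baseline removes most drift in starting temperature, and the washout limits carry-over. Neither deals with a change in the response to heating. Because output followed each subject's reported warmth, such a change is possible, though nothing shows that it was systematic.

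The larger rates in the illustration need a full-SD shift confined to one session; under linear drift at n = 18 the rate stays near 10%. The plan also has minute-by-minute readings, 5-minute intervals and two skin sites, so the rates for the tests actually run may differ. Both points are fair. The bias formula is the firm result and the rates only show scale.

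There is also a trade-off in precision. At n = 18 the unadjusted longitudinal − coplanar estimate has the smaller mean squared error when 0.111 + (4/9)d² < 0.200, that is |d| < 0.45 SD. At n = 36 the limit is 0.32 SD. This arithmetic is correct and would support keeping the adjusted result as a sensitivity analysis if d were known to be small. It is not known, the limit shrinks as the sample grows, and a period term is standard in a crossover analysis.

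Finally, the text is in the past tense, so changing the orders may no longer be possible. The analytic remedy does not depend on that.

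**Conclusion.** The concern holds and should be fixed. The imbalance and the absence of a named session term can be read directly from the plan. The bias is (2/3)d for longitudinal versus coplanar and (1/3)d for each of the other two contrasts, given equal groups and additive session effects.

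The confounding is partial: contraplanar is balanced over sessions, session 1 is balanced over arrangements, and every contrast can be recovered once session is modelled. Whether d differs from zero is unknown, so the plan is exposed to a bias rather than shown to have one. Without a session-adjusted result, a reader cannot separate the two explanations for any difference found.

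**What to change.** **Analysis (usable even if all sessions are complete).** Fit a mixed model with fixed effects for arrangement and session (1, 2, 3) and a random subject effect. Report the session-adjusted arrangement contrasts, Bonferroni-corrected over three, as the primary result, and show the session estimates beside them. Do not substitute order group for session. The cost is one model term and 2 within-subject degrees of freedom, with the standard errors widened as shown in step 3. If order group is also fitted, it uses between-subject degrees of freedom only (2 for three orders, 5 for six).

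**Design (only if allocation has not been run).** Use all six orders, with 3 subjects each per block of 18. This balances session and also which arrangement precedes which, and it removes the precision penalty. A smaller change is to make group B contraplanar, longitudinal, coplanar, which also puts each arrangement once in each session and removes the penalty. In that scheme, however, each arrangement is only ever followed by one other. If first-order carry-over were also fitted at n = 18, its contrast variances would be 0.556σ², against 0.167–0.222σ² for the stated orders and 0.139σ² for six orders. Six orders is therefore the better choice. Either change alters only the randomisation list, and the session term should stay in the model.

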### Participants

Young health male university students, reached through social media, volunteered to participate in the study. Eligible subjects were those that consent in abstain from physical activity at least 24 hours prior to the intervention day, and in avoid caffeine, alcohol, and food intake at least one hour prior to the intervention. Subjects who injured the thigh region in the three months before the study, had circulatory history, cardiac pacemakers, metal implants or external fixation, and self-reported current smoking would be excluded.

### Interventions

Each subject attended to three sessions with a washout period of at least 24 hours. In order to stabilize body temperature, subjects laid in a relaxed prone position on a wooden stretcher, under instruction to refrain from touching the left thigh over the 20 minutes of acclimatization. Then, the previous determined capacitive technic arrangement of SWD was applied for 20 minutes.

The SWD device we used was Diatermede II (Carci® 4022, São Paulo, SP, Brazil), on continuous mode, with a frequency of 27.12 MHz. Which was delivered by means of two pad electrodes (17x12 cm) surrounded by felt and positioned over 1 cm^6 of toweling. On coplanar arrangement, the electrodes were as far apart as the cross-sectional diameter of the pad electrode (Figure 1). We controlled the intensity based on a referred warm heat perception by the subject. The device was calibrated prior to data acquisition.

We measured the temperature in three time points, first: before the application (baseline), after acclimatization period, second: immediately after each application, and third: each minute over 25 minutes after electrodes removal. We maintained room temperature between 23 °C and 25 °C, with a mean humidity of 64% throughout the study. The room had no source of infrared radiation or airflow.

Previously to acclimatization period we had marked each 6 cm over 36 cm from the base of the patella towards the anterior superior iliac spine. We collected skin temperature under the electrode (at the centre of the proximal electrode), and at the thigh centre (6 cm from the proximal electrode's edge). Thus, on coplanar and longitudinal arrangement at 18 cm and 30 cm marks, and on contraplanar arrangement at 12 cm and 24 cm marks (Figure 2).

Outcomes Measures

The primary endpoint was to determine the most efficient arrangement of capacitive technic with respect to temperature change over the 25 minutes after application, which was measured in Celsius (°C) on the anterior aspect of the left thigh.

To collect skin temperature we used an SC325 infrared thermography camera (A325sc; FLIR Systems, [name]), positioned vertically 1 m from the thigh. The camera was calibrated prior to data acquisition. Manufacturers' specifications defined an accuracy of +/- 2%, and emissivity of 0.01 to 1. We analyzed the thermographic images (320 x 240 pixels) using ResearchIR software, version 4.40.1.6 (Copyright © 2016 FLIR Systems, FLIR Systems, Inc., [name]).

#### Statistical Analysis

We used descriptive statistics to summarize data, computing means and standard deviations (SDs) for the primary endpoint, and the Shapiro-Wilk test for checking data normality. To compare the arrangements we conducted a repeated measures analysis of variance (ANOVA) and Bonferroni post-hoc tests. The  $\alpha$  level was set at  $<.05$ . Effect size was calculated through partial eta squared and correlated using Cohen index (.1 to .3 as small, .3 to .5 as medium, and over .5 as large). In order to summarize the data we conducted 5-minute interval analysis. SPSS software (version 20; IBM Corp, Armonk, NY) was used for analyzes.

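### Single-step Bonferroni on the three arrangement pairs is valid but conservative; a step-down test on one fixed set of three comparisons would raise the chance of showing that one arrangement beats both others

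*Combined protocol and SAP*

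**What the plan says.** The Outcomes Measures text, within the Interventions section, frames the aim as a selection: "The primary endpoint was to determine the most efficient arrangement of capacitive technic with respect to temperature change". It does not say what result would justify naming one arrangement.

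Study Design lists three arrangements, given in three orders, the first being "group A) coplanar, contraplanar and longitudinal". Interventions confirms that every subject receives all three: "Each subject attended to three sessions with a washout period of at least 24 hours". There are therefore three within-subject pairs.

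Statistical Analysis names a "repeated measures analysis of variance (ANOVA) and Bonferroni post-hoc tests" with an alpha of .05. It does not mention a step-down or closed procedure, a sphericity correction, a period term, sidedness, or the set of tests to which the .05 applies. It also adds an analysis by 5-minute intervals, and Interventions describes two measurement sites.

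The documents give no sample size, power or expected effect. The nearest figure is the allocation to "three groups with a ratio of 1:1:1 and block sizes of 18".

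**The concern.** Bonferroni in its usual single-step form holds every pair to .0167, whatever the other pairs show. If most efficient is taken to mean better than each of the other two, two rejections are needed and the .0167 threshold must be met twice. A truly best arrangement may then be formally separated from only one competitor, leaving the selection question unanswered.

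Part of that strictness is not needed to hold .05 over three pairs, because equalities among three means are logically linked. At stake is the chance of a clear answer from the same subjects, not the validity of a positive result.

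**Working it through.** **Inputs**

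| Input | Value | Source |
|---|---|---|
| Arrangements, pairs | 3, so 3 pairs | Study Design |
| Alpha | .05; familywise over the three pairs is assumed | Statistical Analysis |
| Per-pair level | .05/3 = .0167; single-step is assumed | Statistical Analysis names Bonferroni only |
| Sidedness | two-sided | assumed |
| N | 18 (one block), also 36; wider range 12 to 54 | assumed |
| Effect | one arrangement better than two equal ones by 0.8 to 1.2 session SD | assumed |
| Winner rule | best is significantly better than both others | assumed reading of the aim |

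The plan states no power figure to reproduce. Its alpha is consistent with Bonferroni: 3 × .0167 = .05.

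**Procedures.** Order the p-values p(1) ≤ p(2) ≤ p(3).
- Bonferroni: reject each pair with p < .0167.
- Holm: p(1) < .0167, then p(2) < .025, then p(3) < .05, stopping at the first failure.
- Shaffer: p(1) < .0167, then each of the other two at .05.

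Every Bonferroni rejection is also a Holm and a Shaffer rejection.

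**Why Shaffer holds .05.** For three means, the number of true equalities can be three, one or none. It cannot be two, because A = B and B = C imply A = C.
- Three true: an error requires p(1) < .0167, with probability at most 3 × .0167 = .05.
- One true: only that pair can be falsely rejected, and it is never tested above .05. Bonferroni tests it at .0167, a third of what is allowed.
- None true: no false rejection is possible.

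This needs no assumed effect size, only valid pairwise p-values.

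**Power for one pair** (noncentral t, N = 18, standardised paired difference .7): .63 at .0167, .69 at .025, .80 at .05. With independent session errors, 1.0 session SD corresponds to 1/√2 = .71 on this scale.

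**Chance that the best beats both others** (20,000 simulated trials per setting, paired t tests, independent session errors, no period effect):

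| N | Effect (session SD) | Bonferroni | Holm | Shaffer | Shaffer minus Bonferroni |
|---|---|---|---|---|---|
| 18 | 0.8 | .25 | .31 | .41 | .16 |
| 18 | 1.0 | .48 | .55 | .66 | .18 |
| 18 | 1.2 | .71 | .77 | .85 | .14 |
| 36 | 0.8 | .70 | .76 | .83 | .13 |

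Repeat runs agreed to within about .01. At N = 18 and 1.0 SD, the best beat exactly one competitor in 32% of trials with Bonferroni and 14% with Shaffer.

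**Range.** Over N = 12 to 54, and also with evenly stepped means, Shaffer gained about 10 to 21 points wherever Bonferroni's chance was roughly 10% to 80%. Outside that range the gain fades. At N = 18 it is 4 points at 0.4 SD and 5 points at 1.5 SD. At N = 36 it is 1 point at 1.2 SD and zero at 1.5 SD.

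**Error check.** At N = 18 and 1.0 SD, the truly equal pair was falsely rejected at .017 (Bonferroni), .034 (Holm) and .049 (Shaffer). Shaffer's familywise error was .039 to .052 over all null and partial-null settings tried.

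**The case against.** Bonferroni is valid, and the plan makes no power claim that it breaks, so this could be called a preference between sound methods. That stands: the point concerns efficiency. Three further objections limit it.

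**The family may be larger than three.** Two sites, five 5-minute intervals and three pairs make 2 × 5 × 3 = 30 comparisons, and no primary set is named. Take ten such families at N = 18, with one arrangement better by 1.2 SD and the other two equal. The chance of at least one false difference for the equal pair is then .15 with Bonferroni and .40 with Shaffer if the families are uncorrelated, .12 and .30 at correlation .5, and .05 and .13 at correlation .9. The step-down claim therefore holds only within one fixed set of three comparisons.

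**The orders are unbalanced.** Across groups A, B and C, coplanar falls in positions 1, 2, 2; contraplanar in 2, 1, 3; longitudinal in 3, 3, 1. With equal groups the mean positions are 5/3, 2 and 7/3, so coplanar and longitudinal differ by 2/3 of a session and a session trend biases an unadjusted paired test. For an illustrative trend of 0.5 SD per session, with contraplanar better by 1.0 SD and the other two equal, false rejection of the equal pair is about .047 with Bonferroni and .111 with Shaffer. For a trend of 1.0 SD it is .087 and .209. The documents give no trend size.

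A reader might infer that Bonferroni's strictness buys nothing. The last two objections show that it does: its unused error acts as slack against extra comparisons and period bias, neither of which the plan handles elsewhere.

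**The winner rule is not in the plan.** Beating both others is one reading of "The primary endpoint was to determine the most efficient arrangement of capacitive technic". The missing rule is a gap in its own right.

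**Conclusion.** The point stands as a cheap efficiency improvement. For one fixed set of three comparisons with valid p-values, a step-down test keeps familywise error at .05 and rejects everything that Bonferroni rejects. The direction of the gain follows from logic. Its size (about .13 to .18 for Shaffer in the four tabulated settings, near zero at the extremes of power) rests on assumed N, effects and two-sided tests, and on no period effect. It was computed for unadjusted paired tests, so the absolute power will differ under a period-adjusted model.

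A reader might go further and conclude that the planned tests are wrong, or that this trial will often fail to name a winner. The documents support neither. Bonferroni controls its error, and without a sample size or expected effect no one can say how often a winner would be missed.

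**What to change.** In Statistical Analysis, first fix one primary comparison set: one measurement site and one summary of temperature change over the 25 minutes. Then replace the Bonferroni post-hoc wording with:

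> The three pairwise comparisons, from a model with period terms, are tested in order of p-value, the smallest at .0167 and, if it is significant, the other two at .05 (Shaffer step-down; Holm as the simpler alternative), without an omnibus F gate. An arrangement is called most efficient only if it is significantly better than both others. The other site and the 5-minute intervals are secondary and outside this .05.

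The model should not force equal variances of the pairwise differences, since the error bound needs each p-value to be valid. An omnibus gate adds a risk if the pairs are then tested at .05: with one arrangement's SD three times the others, an uncorrected F gate gave a familywise error of about .064, and the plan names no sphericity correction.

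The cost is a few lines of text and no extra subjects. The downsides are the lack of simple matching simultaneous intervals (the plan mentions none) and less slack than Bonferroni against bias or extra comparisons, so the primary set and period terms should come with the change. The document is written in the past tense. If results have already been analysed, the step-down result should be labelled post hoc and shown beside the planned Bonferroni result.
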